1.3 JUSTIFICATION

This study is framed within the European Community framework on substances that can have an impact on the health and well-being of the population, focusing on their identification, quantification, monitoring and prevention. The population susceptible to treatment of this kind is almost universal. Companies are investing in improvements in this respect, incorporating substitutes to bisphenols, with effects yet to be confirmed, generating a very dynamic and growing market. The literature demands more solid results and improvements in protocols. The Supramolecular Analytical Chemistry (SAC) research group at the University of Cordoba has developed an innovative, sustainable, specific and more economical method based on the use of supramolecular solvents (SUPRAS) combined with high performance liquid chromatography-high performance mass spectrometry (HPLC-HRMS/MS). This method allows the identification of compounds (known and unknown) by covering a wider range of substances present in the materials under study than solvents.

organic waste cannot be dealt with. Given that this method has not yet been implemented in dentistry, despite being amply tested, this pilot study has been developed to lay the foundations of a protocol, and to have a more exact and extensive knowledge of our treatments. One of the most widely used, especially after the pandemic, is the Michigan type acrylic splint, as a treatment for bruxism. It is also a removable device, which is used at least 6-8 hours a day, and does not involve the use of additional plastic materials that could be other sources of additives, such as cements, sealants or dental temporaries, as is the case with fixed prostheses. The population eligible for such treatment must have completed their bone and tooth growth (18 years of age or older). In the present study, two forms of manufacture were chosen: conventional and printed. The reason for not choosing the milled ones is because the latter generate more waste, and their mechanical response as well as the patient's preference are not better. Therefore, identifying the substances released by the acrylics, using SUPRAS and HPLC-HRMS/MS, by contrasting the *in vitro* and *in vivo* results, may shed some light on this issue.

1.4 OBJECTIVES

There is no evidence of release of substances of particular concern, or endocrine disruptors released from Michigan type acrylic occlusal splints.

General objectives: To describe and quantify the values of substances of very high concern (SVHC) or endocrine disruptors (ED) released from printed or injected acrylic Michigan type splints.

Specific objectives:

1. To identify the SEPs and EDs released by Michigan-type splints made by injection or *in vitro* impression technique, simulating oral environment and wear.
2. Identify SEPs and EDs in saliva released from printed or saliva-injected acrylic Michigan type splints before, during and after insertion in the mouth.
3. To quantify the levels of SEP and ED in saliva released from printed or injected acrylic Michigan type splints in saliva before, during and after insertion in the mouth.
4. Contrast the results obtained in the laboratory test with those recorded in the saliva samples of the *in vivo* study.

5. Relate the results to the manufacturing process, stage of exposure, time, habits and individual characteristics of each volunteer.

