The main problem when studying the presence of additives released by dental materials in the organism is the extraordinary difficulty in associating them explicitly to this type of device, given that they are commonly found in our surroundings. Their multiple origins: environmental, nutritional, hygienic sources, etc., make it extremely difficult to associate the origin with the substance identified. For this reason, in vitro studies are a widely used method. However, the protocols developed to date show a certain lack of uniformity: in some, discs are analysed without considering the inhibited layer, in others their polishing does not correspond to the clinical protocol, or there is a lack of uniform extraction ratio, or the solvents are different, or salivary turnover is not taken into account (the possible alterations in its composition, pH, viscosity, or flow that may occur in the same subject, and its role in the chemical erosion of the material). On the other hand, in some of these tests, occlusal wear is not considered. They provide data on quantification and identification of the substances in saliva, mainly bisphenols, substitutes for

and phthalates, in different materials, depending on their manufacturing technique (milled, printed, injected), and their curing (thermo-, self-, photopolymerised). Clinical studies focus on paired samples, or on epidemiological, retrospective descriptive, comparative, retrospective and prospective studies where saliva, blood and urine samples are analysed to determine their assimilation. Among the methodologies used, the FDA (Food and Drug Administration) recommends High Performance Liquid Chromatography (HPLC) or Gas Chromatography (GC). Authors such as Hampe Tristan, advise Mass Spectrometry (MS), or the HPLC/MS tandem, establishing as ideal the combination of High Resolution Mass Spectrometry (HRMS) and MS, since it does not detect products such as Bis GMA, -EMA and -UDMA (De Angelis et al., 2022; Hampe et al., 2022; Kessler et al., 2020; Tichy et al., 2021). (Francisco et al., 2022; Van Landuyt et al., 2011a, 2011b; Vervliet et al., 2022; Wedekind et al., 2021).

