2 METHODOLOGY OF THE STUDY

2.1 DESIGN

This is a prospective analytical observational experimental pilot study that aims to analyse the substances of particular concern and endocrine disruptors detected in saliva, released by conventional dental devices, before and after the intervention. They will therefore be paired samples, where the control group will be the same subject, minimising the independent variables: saliva pH, microbiome, salivary flow, habits, occlusal wear, erosion by external agents and saliva.

Saliva sampling shall be carried out in accordance with the conventional protocol RD 1716/2011. The saliva containers shall comply with the requirements of the ISO 6717:2021 standard. They shall be packaged and transported according to the protocol Order JUS/1291/2010 of 13 May. All samples shall be identified with the number assigned to the volunteer, time, material and type of manufacture (processed, machined or printed), and shall be sent to the Chemical Institute for Energy and Environment (IQUEMA). University of Cordoba, where they will be analysed by the SAC group, for subsequent statistical treatment and interpretation.

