Thus, knowing the possible elements identified, the saliva samples can be treated. This is carried out with a volatile supramolecular solvent spontaneously synthesised by adding hexanol and tetrahydrofuran. The methodology to be followed is the same as previously described in the *in vitro* phase.

Dependent variables: substances of very high concern and endocrine disruptors. Independent variables: usual residence, type of manufacture (printed or injected), time, age, type of polymerisation.

After identification and quantification of the detected substances, the data will be collected in a database with the volunteer's information (ANNEX IV).

Finally, the results will be analysed and correlated with those obtained in the experimental laboratory phase, and the possible participating variables: age, type of material, type of manufacture and habits of the participant (figure 2).

[figure not shown]

Figure 2. Timeline of *in vivo* pilot study on substances released from injected or printed acrylic occlusal splints. University Polyclinic of the European University of Madrid.

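### Objectives 2 and 3 word pre-insertion saliva findings as splint release, against the own-subject control in 2.1, and release is never referred to Time 0

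*Protocol*

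**What the plan says.** The general objective in 1.4 is "To describe and quantify the values of substances of very high concern (SVHC) or endocrine disruptors (ED) released from printed or injected" splints. Specific objective 2 is "Identify SEPs and EDs in saliva released from printed or saliva-injected acrylic Michigan type splints before, during and after insertion in the mouth". Specific objective 3 begins "To quantify the levels of SEP and ED in saliva released from printed or injected acrylic Michigan type splints" and ends with the same three periods.

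Section 2.1 describes the substances as "detected in saliva, released by conventional dental devices, before and after the intervention", and continues: "They will therefore be paired samples, where the control group will be the same subject". Section 2.6.1 places Time 0 before the intervention. At Appointment 4 one saliva sample precedes the fitting and adjustment of the splint and another follows.

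Section 1.2 says that tying these substances to a dental device is the main difficulty, "given that they are commonly found in our surroundings".

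In 2.6 the outcome is given as "Dependent variables: substances of very high concern and endocrine disruptors", with time and type of manufacture among the independent variables. Annex IV has a concentration column for each of saliva samples 0 to 3. Section 2.8 plans frequencies with 95% confidence intervals, chi-square or Fisher tests, Student's t or Mann-Whitney tests, and logistic regression for an odds ratio of seroprevalence, a term the protocol does not define.

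**The concern.** The central quantity of the study is a substance released from the splint, and the text gives the Time 0 sample two roles in it. Read literally, the objectives make Time 0 one of the occasions on which release is identified and measured. Under 2.1 the same sample is the control against which release would be judged. It cannot be both.

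The later sections do not settle the matter in favour of 2.1. Neither the dependent variable in 2.6 nor any analysis in 2.8 is expressed relative to Time 0.

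Two results are at stake. First, a volunteer already positive from diet, hygiene products or the environment can be counted in a release frequency. Second, such volunteers are positive in both manufacturing groups whatever the splint does, so an odds ratio built on raw detection moves towards 1.

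**Working it through.** **Does the text refer release to Time 0?**

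- 1.4, objectives 2 and 3: release is attached to the period before insertion as well as to the later ones.
- 2.1: the same attachment, followed by a paired design with the subject as control. Time 0 is not named as the control, but before-and-after sampling implies it.
- 2.6: the outcome is the substances, with no change from Time 0 and no detection rule. Time is an independent variable, so a comparison with Time 0 is possible but not specified.
- 2.8: no analysis is stated relative to Time 0. Mann-Whitney is for independent samples, the form of the t-test is not given, and no paired test is named.
- Annex IV: the Time 0 concentration is recorded, so a baseline-referenced value can be computed.

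**How much could it matter?** The protocol states no background rate, release rate or effect size, so there is no figure of its own to reproduce. The rates below are assumptions. From 2.4: 15 volunteers per group, 30 in all.

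Assumptions: background detection b is equal in both groups, stable over time and free of assay error. Among Time 0 negatives the splint causes detection in r = 10% (injected) and 30% (printed).

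Formulas:
- Raw detection after placement = b + (1 − b)r.
- New detection in all volunteers = (1 − b)r.
- Odds ratio = [p(printed)/(1 − p(printed))] / [p(injected)/(1 − p(injected))].
- Overall percentages are the mean of the two equal groups.

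Worked case, b = 40%:
- Raw: 0.4 + 0.6 × 0.1 = 46% and 0.4 + 0.6 × 0.3 = 58%. Overall 52%. Odds ratio (0.58/0.42)/(0.46/0.54) = 1.62.
- New detection in all volunteers: 6% and 18%. Overall 12%. Odds ratio (0.18/0.82)/(0.06/0.94) = 3.44.
- Among Time 0 negatives, for any b: (0.3/0.7)/(0.1/0.9) = 3.86.

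| b | Raw, injected v printed | Raw overall | Raw OR | New, injected v printed | New overall | New OR, all volunteers | OR, Time 0 negatives |
|---|---|---|---|---|---|---|---|
| 20% | 28% v 44% | 36% | 2.02 | 8% v 24% | 16% | 3.63 | 3.86 |
| 40% | 46% v 58% | 52% | 1.62 | 6% v 18% | 12% | 3.44 | 3.86 |
| 60% | 64% v 72% | 68% | 1.45 | 4% v 12% | 8% | 3.27 | 3.86 |
| 80% | 82% v 86% | 84% | 1.35 | 2% v 6% | 4% | 3.13 | 3.86 |

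The 3.86 describes Time 0 negatives only. The like-for-like comparison with the raw odds ratio, in all volunteers, is 3.63 to 3.13.

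Null case, r = 0 in both groups: an any-detection rule would label 30b volunteers as showing release, which is 3, 9, 15, 21 and 27 of 30 for b = 10%, 30%, 50%, 70% and 90%. A rule based on new detection would label none, given stable background and no assay error.

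**The case against.** The strongest reply is that the phrase in the objectives is loose wording for the sampling times. Section 2.1 uses nearly the same phrase and at once concludes that the samples are paired, so the authors evidently had a before-after comparison in mind. Time is listed as an independent variable, and objective 5 relates results to stage of exposure and time. Annex IV is a collection form and properly holds raw values. The laboratory phase first identifies what the splint material releases, and objective 4 contrasts that with saliva. Derived-variable rules usually sit in an SAP, which is not shown.

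Much of this stands. A reader might infer that the protocol scores any detection as release and counts background as splint release. It contains no such rule, and the paired design leaves room to correct for background. The absence of a detailed algorithm is not the point either.

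Two parts do not answer the concern. The laboratory phase narrows which substances are looked for, but a compound found in the acrylic can also reach saliva from other sources, as 1.2 accepts. And an SAP implements the objectives. Here the objectives themselves conflict with the design, and 2.8 does not resolve it.

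**Conclusion.** The concern holds in a limited form. Objectives 2 and 3 attach release to a sample taken before the splint is in the mouth, against the own-subject control in 2.1. The outcome in 2.6 and the analyses in 2.8 are not referred to Time 0. Background exposure can therefore be reported as release, and a between-group odds ratio based on raw detection can be attenuated. Whether either would happen is not fixed by the text.

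The size is illustrative only. Under the assumed rates, raw detection overstates new detection (36% to 84% against 16% to 4%), and the odds ratio falls to between 2.0 and 1.3. This depends on the outcome being analysed as binary, on equal and stable background, and on the chosen 10% and 30%. Other rates change the figures but not the direction, provided background is similar in the two groups and the splints differ. This is more than an editorial slip, because it concerns the quantity the study sets out to measure.

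**What to change.** - Reword objectives 2 and 3 so that Time 0 describes background and release is assessed at Times 1-3 relative to Time 0. Align the matching phrase in 2.1.
- For concentrations, use the within-subject change from Time 0, or the later value adjusted for the Time 0 value, and compare this between injected and printed splints.
- For detection, define the event per substance as new detection among volunteers negative for that substance at Time 0. Use it for the release frequencies and for any binary model, in place of the undefined seroprevalence. Keep raw detection by time point as description.
- Do not classify every rise above assay repeatability as release. Section 1.2 notes that saliva composition and flow can vary within one subject and that other sources are multiple, so ordinary fluctuation would be counted.

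The cost is wording and one derived variable from columns already in Annex IV, with no new data. Reported release frequencies may be lower. The binary analysis uses fewer volunteers: 30 × (1 − b), or an expected 24, 18, 12 and 6 of 30 at assumed background of 20%, 40%, 60% and 80%. For common substances the concentration analysis will therefore carry most of the information.

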2.6 DESCRIPTION OF THE STUDY

2.6.1 VOLUNTEER RECRUITMENT:

The study groups will be formed in accordance with the requirements and inclusion criteria. Each of the subjects will be informed of the purpose and methodology of the project by means of an information document for the volunteer (Appendix II) and must sign the informed consent form provided for this purpose (Appendix III); they may withdraw from participation at any time. The data of the participants will be stored in a clinical history with an individual key number, in accordance with the regulations contained in the current Organic Law 3/2018, of 5 December, on the Protection of Personal Data.

Appointments will be made as follows:

APPOINTMENT 1: A conventional computerised clinical history is taken of the patient, in which data is collected on general health, orofacial and nutritional habits and hygiene. We explain in detail what the treatment consists of: Michigan type relaxation splint (device to prevent tooth wear due to bruxism). Each intervention is governed by scientific and deontological criteria, respecting all the ethical rules of research. The following is a detailed description of the study, its duration and methodology. The four moments of saliva collection will be explained: before, during, and 3 and 6 months after placement, as follows:

-Time 0: the day of the appointment, before the intervention.

-Step 1: On the day of the appointment, device placement.

-Time 2: 3 months after device placement.

-Time 3: 6 months after treatment.

Information and informed consent will be provided.

APPOINTMENT 2: Preparation and taking of models for the Michigan type splint according to the conventional protocol for this treatment.

APPOINTMENT 3: The models will be assembled in the articulator to send and request the making of the splint, specifying whether it is injected or printed.

APPOINTMENT 4: A saliva sample is taken in the device for this purpose. After checking for proper fit and retention, the occlusal adjustments will be made with a handpiece and conventional acrylic and polishing burs. After completion of the procedure, a new saliva sample shall be taken. The samples shall be identified with the patient's assigned code and stored according to conventional standards. An appointment will be made after 6 months to continue with the study and in accordance with the check-up times for correct oral health.

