ANNEX IV

Voluntary code	CONCENTRATIONS	CONCENTRATIONS	CONCENTRATIONS	CONCENTRATIONS
	M. Saliva 0	M. Saliva 1	M. Saliva 2	M. Saliva 3
SUBSTANCES				

 Name, surname, ID number and signature of the researcher _____
Date

Sample collection table for each volunteer

VARIABLES	Volunteer 1	Volunteer 2	Volunteer 3	Volunteer 4	Volunteer 5
AGE	-				
GENDER (MALE, FEMALE, OTHER)					
MATERIAL (ACRYLIC)					
MANUFACTURING (INJECTED or PRINTED)		-			
USUAL RESIDENCE (URBAN, RURAL)			-		
EXPOSURE TIME (HOURS) BRUXIST (YES/NO)				-	
REFLUX (YES/NO)					
ANTIDEPRESSANTS (YES/NO)					
ANTIHISTAMINES (YES/NO)					
DECONGESTANTS (YES/NO)					

BIBLIOGRAPHY

- Alhazzawi, T. F. (2016). Advancements in CAD/CAM technology: Options for practical implementation. *Journal of Prosthodontic Research*, *60*(2), 72-84.
<https://doi.org/10.1016/J.JPOR.2016.01.003>
- Alharbi, H. F., Algonaiman, R., Alduwayghiri, R., Aljutaily, T., Algheshairy, R. M., Almutairi, A. S., Alharbi, R. M., Alfurayh, L. A., Alshahwan, A. A., Alsadun, A. F., & Barakat, H. (2022). Exposure to Bisphenol A Substitutes, Bisphenol S and Bisphenol F, and Its Association with Developing Obesity and Diabetes Mellitus: A Narrative Review. *International Journal of Environmental Research and Public Health*, *19*(23).
<https://doi.org/10.3390/ijerph192315918>
<https://doi.org/10.1016/J.ADDMA.2020.101693>
- Bisphenol A and incisor molar hypomineralisation:: A review - Dialnet* (n.d.). Retrieved June 17, 2023, from <https://dialnet.unirioja.es/servlet/articulo?codigo=7998248>
- Carneiro Pereira, A. L., Bezerra de Medeiros, A. K., de Sousa Santos, K., Oliveira de Almeida, É., Seabra Barbosa, G. A., & da Fonte Porto Carreiro, A. (2021). Accuracy of CAD-CAM systems for removable partial denture framework fabrication: A systematic review. *Journal of Prosthetic Dentistry*, *125*(2), 241-248.
<https://doi.org/10.1016/j.prosdent.2020.01.003>

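### No splint size is recorded, so laboratory release cannot be scaled to a volunteer's splint, and a size difference between printed and injected splints could not be told from a difference in release per unit of acrylic.

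*Protocol*

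**What the plan says.** **Aims.** The general objective (section 1.4) is to describe and quantify what the splints release. Objective 3 quantifies levels in saliva. Objective 4 is to "Contrast the results obtained in the laboratory test with those recorded in the saliva samples of the" in vivo study. Objective 5 relates results to the manufacturing process, among other factors. Section 1.3 also gives the contrast an identification purpose: "identifying the substances released by the acrylics, using SUPRAS and HPLC-HRMS/MS, by contrasting the" in vitro and in vivo results.

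**Planned use.** Section 2.6 ends the laboratory phase with quantification of the prioritised compounds. It then says that "the results will be analysed and correlated with those obtained in the experimental laboratory phase, and the possible participating variables: age, type of material". The list goes on to name the manufacturing process and the participant's habits.

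**What is recorded.** The variable list in section 2.6 reads "Independent variables: usual residence, type of manufacture (printed or injected), time, age, type of polymerisation". In Annex IV the saliva outcome is a concentration at samples 0 to 3. The splint is described by its material and by the line beginning "MANUFACTURING (INJECTED or PRINTED"; exposure hours are recorded as well. Weight, area and thickness appear in neither place.

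**What the protocol knows about the issue.** Section 1.2 faults earlier in vitro work because "there is a lack of uniform extraction ratio, or the solvents are different, or salivary turnover is not taken into account". At Appointment 4 (section 2.6), "the occlusal adjustments will be made with a handpiece and conventional acrylic and polishing burs".

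**The concern.** A leachate concentration depends on how much acrylic meets how much liquid. The protocol makes this criticism of earlier laboratory work, but collects nothing that would give the amount of acrylic in each volunteer's mouth. That amount is individual, because the splint is custom-made and then ground.

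Two results are at stake. In Objective 4, a laboratory amount cannot be turned into an expected amount for a given volunteer. In Objective 5, a process that gives larger splints would appear to release more even if each gram released the same.

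This gap lies in data collection. A statistical analysis plan written later cannot recover a weight that was never taken. The size at insertion is also lost after fitting, because further adjustments are allowed at Appointments 5 and 6.

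**Working it through.** The plan gives no figure on this point to reproduce. The check is a reading of what is recorded, a simple model, and an illustration on assumed inputs.

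**1. Search for a size measure.** The objectives, the variable list and appointments in section 2.6, section 2.8 and Annex IV contain no splint weight, area, thickness or amount ground away. Saliva volume and flow are not recorded either. The text states no laboratory ratio of material to liquid, but Figure 1 is not shown and may hold one.

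**2. What the data can identify.** For volunteer *i* with process *m*, write

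C_i = B_i + r_m × A_i / V_i

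where B is background from other sources, r is release per unit of acrylic, A is the amount of acrylic and V is the diluting saliva volume. Subtracting sample 0 removes B (if it is stable) and leaves r_m × A_i / V_i. No splint is in place at sample 0, so pairing does not remove A.

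- *Objective 5:* with similar V in the two groups, the ratio of group means is about (r_P / r_I) × (A_P / A_I), for printed (P) and injected (I). Only the product can be estimated. Random allocation, which the available text does not state, would not separate the two factors if size follows from the process.
- *Objective 4:* the laboratory informs r, while saliva reflects r × A / V. Section 2.6 describes the laboratory phase as testing the material. If that yields one value per substance and material, all volunteers with the same material share one laboratory value, and a correlation across volunteers mostly restates the manufacturing contrast. Recording A lets the expected dose r × A vary between volunteers. V remains unknown, so the dose is relative.

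**3. Illustration for Objective 5.** From the protocol: 15 per group (section 2.4) and significance at 0.05 (section 2.8), taken as two-sided. Assumed: equal r in both groups, baseline-corrected concentration proportional to A, log-normal values and a normal approximation.

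- SD on the log scale: s = √ln(1 + CV²)
- SE = s × √(2/15)
- z = ln(size ratio) / SE
- Probability of p ≤ 0.05 = Φ(z − 1.960) + Φ(−z − 1.960)

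Example with ratio 1.2 and CV 50%: s = √ln 1.25 = 0.472; SE = 0.472 × 0.365 = 0.172; z = 0.182 / 0.172 = 1.057; probability = 0.1833 + 0.0013 = 0.185.

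| Mean size difference | CV 30% | CV 50% | CV 80% |
|---|---|---|---|
| 10% | 0.144 | 0.086 | 0.066 |
| 20% | 0.398 | 0.185 | 0.109 |
| 30% | 0.687 | 0.331 | 0.175 |
| 50% | 0.966 | 0.652 | 0.352 |

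With no size difference the probability is 0.05.

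**4. Effect of background.** If only a share *w* of the measured concentration comes from the splint, a 20% size difference moves the uncorrected total by w × 20%. With w = 0.5 (assumed), that is 10%.

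**5. Random size variation.** If size varies with CV 20% independently of other variation (assumed), the CVs combine as √[(1 + CV₁²)(1 + CV₂²) − 1]. From 50%: √(1.25 × 1.04 − 1) = 55%. From 80%: √(1.64 × 1.04 − 1) = 84%. This is modest extra noise, not bias.

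**The case against.** The best defence is that the contrast mainly serves identification. Section 1.3 says so, the laboratory phase builds the compound list used for the saliva samples, and Objective 4 names no quantitative agreement. Detection, rank order and profile within a material need no splint size. This stands, and it rules out the inference that the two sets of results cannot be compared at all. It does not remove the point, because section 2.6 also plans quantification in both phases and a correlation.

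A reader might also infer three stronger things that the documents do not support:

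- *That the manufacturing contrast is biased, one for one with size.* No document gives splint sizes, so a difference between processes is only possible. Section 1.2 says these substances have many other sources, and step 4 shows that background dilutes the effect on uncorrected values.
- *That the laboratory extraction ratio is missing.* Figure 1 covers the in vitro phase and cannot be seen here.
- *That recording size would put both arms on one absolute scale.* It would not, because saliva volume and flow are also unrecorded.

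Finally, if one process systematically yields thicker splints, size is a consequence of manufacture and part of what the wearer is exposed to. Adjusting for it could remove part of the effect that Objective 5 asks about. This stands and shapes the fix.

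**Conclusion.** The point holds in this form: the protocol plans a quantitative link between laboratory and saliva, and a comparison by manufacturing process, without recording splint size. The qualitative part of Objective 4 is unaffected. In the quantitative part, laboratory release cannot be scaled to the individual splint. In Objective 5, a difference in size could not be told apart from a difference in release per unit of acrylic.

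The size of the second problem is unknown. On the assumptions in step 3, a 10% mean size difference raises the chance of a declared manufacturing difference from 0.05 to between 0.066 and 0.144, and a 30% difference to between 0.175 and 0.687, over CVs from 80% to 30%. These figures rest on proportional release, baseline-corrected values and assumed CVs; uncorrected background would lower them. The change is worth making because it is cheap and the size at insertion cannot be recovered later, not because bias has been shown.

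**What to change.** 1. At Appointment 4, after occlusal adjustment and before the post-placement saliva sample, weigh every dry splint on the same balance in both groups. Add the weight to Annex IV.
2. Express laboratory release per gram of acrylic and state the ratio of material to liquid, unless Figure 1 already does. Use release per cm² only if area is measured the same way in both groups. A design file for printed splints predates the grinding, and using it in one group only would tie measurement error to manufacture.
3. In the Objective 4 correlation, use weight × laboratory release as each volunteer's relative expected dose. State that, without saliva volume or flow, the comparison is of relative dose and not of absolute concentration.
4. Keep the unadjusted per-splint manufacturing contrast as the main one. Add a weight-adjusted contrast as a supporting analysis, and say that size may itself result from manufacture.

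The cost is one form field and a short weighing per splint, with no extra visit or patient procedure. Two limits remain: weight only approximates exposed surface, and one weight at fitting does not follow grinding at later visits.
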